15.1 Analysis of Physiologic Effects (Lung Function)

The primary goal of the current study is to determine the effects of Aerospan on lung function in children with small airway obstruction. Participants recruited into this randomized parallel group study will be randomly assigned to either receive (1) 80 mcg of Aerospan twice a day or (2) 160 mcg of Aerospan twice a day, during the six-week study period. Outcomes will be measured at baseline and at six-week follow-up as described above.

First we will start with straightforward tests for differences among the two groups to test if our randomization scheme was successful. Analysis of Variance (ANOVA) techniques will be used to test for difference among continuous variables, while Kruskal-Wallis, Fischer's Exact Tests and Wilcoxon methods will be used to test for differences among categorical variables.

The primary endpoint will be changes in outcomes, over time, from baseline to six-week follow-up. The change in scores from baseline to six-week follow-up will initially be compared using paired t-tests and Chi-squared tests for trend. Repeated measurements will be analyzed using generalized linear mixed-effects regression modeling (GLMM) techniques. For continuous outcomes (e.g., FEV1, FEF 25-75%, Fres, X5, AX, R5-R20.) the identity link function and normal distribution will be used. For count data (e.g., use of Beta-agonists, episodes of

coughing, episodes of wheezing, etc.) the log link function and the Poisson distribution will be used. If we dichotomize outcomes (e.g., a Beta-agonist was used, coughing occurred, etc.) the logit link function and Bernoulli distribution will be used. Statistical analyses will be performed using SAS® Version 9.3 (SAS Institute Inc., Cary, NC).

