MDI	Metered Dose Inhaler
PI	Principal Investigator
SAE	serious adverse experience

PROTOCOL SYNOPSIS

TITLE	Flunisolide HFA in Children with Small Airway Disease
FUNDING AGENCY	MEDA Pharmaceuticals
PRINCIPAL INVESTIGATORS	[name] University of Louisville Louisville, KY [name] University of Louisville Louisville, KY
PRINCIPAL INVESTIGATOR SPONSOR	MEDA Pharmaceuticals
DATA COORDINATING CENTER	University of Louisville Physicians – Pediatric Pulmonology (Academic Office)
NUMBER OF SITES	One
STUDY DESIGN	Prospective, randomized, parallel, open label study
OBJECTIVE	To assess whether there is a dose-related difference with flunisolide HFA in pediatric patients with small airway obstruction based on pulmonary function parameters specifically designed to measure changes in small airway function.
NUMBER OF SUBJECTS	50

SUBJECT ELIGIBILITY CRITERIA	
Inclusion Criteria:
 
1. Diagnosis of asthma by pediatrician or asthma specialist2. Informed consent by parent or legal guardian3. 6 years to 21 years of age at Screening Visit4. Ability to comply with medication use, study visits and study procedures as judged by the site investigator5. $\text{FEF}_{25-75\%} < 65\%$ of predicted as a marker for small airway disease 
Exclusion Criteria:
 
1. Acute wheezing at Screening visit or at Baseline visit2. Acute intercurrent respiratory infection, defined as an increase in cough, wheezing, or respiratory rate with onset in 1 week preceding Screening visit or 3 weeks preceding Baseline visit3. Oxygen saturation $< 94\%$ at Screening visit or at Baseline visit4. Clinically significant upper airway obstruction as determined by the Site Investigator (e.g. severe laryngomalacia, markedly enlarged tonsils, significant snoring, diagnosed obstructive sleep apnea)5. Severe gastroesophageal reflux, defined as persistent frequent emesis despite anti-reflux therapy6. Physical findings that would compromise the safety of the subject or the quality of the study data as determined by site investigator7. ICS use within 7 days of Baseline visit, systemic steroid use within 30 days of Baseline visit8. CF, ILD, history of severe BPD or other underlying significant respiratory disease apart from asthma9. Patients who are pregnant may not enroll in this study

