1 BACKGROUND

Flunisolide HFA is an inhaled corticosteroid that is a reformulated version of the older CFC preparation. The CFC formulation was approved in 1981 and had been in use as an asthma controller since with good results.¹ The HFA formulation, which is in solution as opposed to suspension, has superior lung deposition when compared to its CFC counterpart (68% versus 20%).¹ Studies have demonstrated flunisolide HFA's effectiveness with regards to controlling airway inflammation and improving lung function^{2,3} while maintaining an excellent side effect profile, including no measurable effect on growth over one year.⁴ These attributes make it ideal for use in pediatric patients in whom growth suppression is a common concern. In addition, the current device used for delivery has a built-in spacer to ensure optimal lung deposition.

It is known that flunisolide HFA is uniformly distributed throughout all airways, with deposition approaching 68% and less drug being deposited in the oral cavity than larger molecule inhaled corticosteroids. Fluticasone, for example, has a larger particle size and results in about 20% lung deposition, mainly in the central airways. Despite this, there is little data that specifically examines the effect of flunisolide HFA on small airway parameters in children with asthma. We propose a randomized parallel study between flunisolide HFA 80 mcg twice a day and 160 mcg twice a day to determine the effect of each dose on spirometry and impulse oscillometry (IOS) parameters.

Based on the small molecule size and even lung deposition, we hypothesize that we will see a dose dependent significant improvement in small airway parameters (FEF 25-75%, AX, Fres, X5, R20-R5) with flunisolide. Secondary outcome measures will include clinical effects such as frequency of coughing and wheezing, number of short acting beta agonists used, oral steroid doses required, emergency department visits, and hospitalizations. If the results support our hypothesis this will address an important problem in the field and shift current clinical practice paradigms by a refinement in interventions. It may also provide the foundation for future studies to directly compare flunisolide to other coarse molecules inhaled corticosteroids.

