Adult and Adolescent Patients 12 Years of Age and Older: Efficacy was evaluated in 669 asthma patients, 12 to 78 years of age, including 88 patients 12-17 years of age and 581 patients 18 years and older. Mean FEV1 at screening was 2.44 L and mean FEV1 at baseline was 2.72 L following the 2-week run-in period. Patients were randomized to AEROSPAN Inhalation Aerosol 80 mcg, 160 mcg or 320 mcg twice daily, flunisolide CFC inhalation aerosol 250 mcg, 500 mcg, or 1000 mcg twice daily, or placebo. Change from baseline in percent predicted FEV1 over 12 weeks treatment demonstrated that placebo patients deteriorated 4.3% from baseline after 12 weeks of treatment, whereas patients treated with AEROSPAN Inhalation Aerosol 160 mcg or 320 mcg twice daily maintained FEV1 over the course of the study. Results for the comparison to placebo were statistically significant for the 160 and 320 mcg twice daily AEROSPAN Inhalation Aerosol doses (see Figure 1), but not for the 80 mcg dose. Secondary endpoints of AM peak expiratory flow rate, AM and PM asthma symptoms, nocturnal awakenings requiring a β 2 agonist, and as needed use of inhaled β 2 agonists showed differences from baseline favoring AEROSPAN Inhalation Aerosol over placebo. AEROSPAN Inhalation Aerosol and flunisolide CFC inhalation aerosol gave comparable results.

Pediatric Patients 4 to 11 Years of Age: The trial enrolled 583 asthma patients, 4 to 11 years of age, although the primary efficacy parameter was evaluated only in the population of 513 patients 6 to 11 years of age. In these patients, the mean FEV1 at screening was 81.2% predicted, and the mean FEV1 at baseline following a two week run-in period was 87.5% predicted. Patients were randomized to

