AEROSPAN Inhalation Aerosol 80 mcg or 160 mcg twice daily, flunisolide CFC inhalation aerosol 250 mcg or 500 mcg twice daily, or placebo. Change from baseline in percent predicted FEV1 over 12 weeks in patients 6 years of age and older demonstrated that placebo patients deteriorated 4.0% from baseline after 12 weeks of treatment; whereas patients treated with AEROSPAN Inhalation Aerosol 80 mcg or 160 mcg twice daily maintained FEV1 over the course of the study. Results for the comparison to placebo were statistically significant for the 80 mcg and 160 mcg doses of AEROSPAN Inhalation Aerosol, but there was no added benefit for the 160 mcg BID dose over the 80 mcg BID dose (see Figure 2). AEROSPAN Inhalation Aerosol and flunisolide CFC inhalation aerosol gave comparable results in patients 6 years of age and older.

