3 STUDY OBJECTIVES

3.1 Primary Objective

To assess the impact on lung function of two different doses of HFA flunisolide in asthma patients with small airway disease

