4 STUDY DESIGN

4.1 Study Overview

This is a single center, open label, parallel group trial comparing the efficacy of two different strengths of HFA flunisolide on lung function in asthma patients with small airway disease. We will enroll approximately 50 pediatric patients (ages 6-18, see discussion on sample size below) with mild to moderate asthma based upon the National Heart, Lung, and Blood Institute asthma guidelines.²¹ These patients will be recruited from new patients presenting to a pediatric pulmonary clinic as well as from general pediatric clinics associated with the University of Louisville, School of Medicine. Patients will have been steroid-naïve for at least four weeks. Prior to enrollment, patients will have demonstrated small airway disease based on pre-bronchodilator FEF_{25-75%} of less than 65% predicted.²² Patients will be randomized to receive flunisolide at either 80mcg twice a day or 160mcg twice a day with every other consecutive patient receiving alternating therapy (Figure 1). Prior to starting therapy, baseline IOS and spirometry pre and post bronchodilator (BD) will be obtained (Table 1). Patients will be randomized as described above and will be followed up at six weeks. At that point, repeat IOS and spirometry will be obtained again.

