15.2 Sample Size

Based on our preliminary studies, we anticipate that 10% of all potential participants will not be eligible and/or willing to participant; and that 10% of the eligible/willing participants will be lost to follow-up. Therefore, we will recruit a total of n=50 individuals for the current study. This is a feasible sample size for the research team to recruit and enroll in the current study. Power calculations were based on the anticipated total sample size (n=40) that will be available for complete analysis.

We will develop separate mixed-effects general linear models for each of the continuous outcomes. From the anticipated sample size (n=40) the study has 86% power to detect a 10% main effect of each treatment for each outcome, our anticipated effect size given preliminary studies. When using count data the study has 94% power to detect a 10% decrease in the rate of outcomes (coughing, wheezing, etc.), our anticipated change in the rate. Using the dichotomized version of some outcomes, this study has 80% power to detect on odds ratio of 1.32 with a two sided $\alpha=0.05$ (n=40). Therefore, we have more than sufficient numbers of participants in each comparison group.

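### Section 15.1 sets the effect of Aerospan itself as the primary goal and tests within-patient change first, but two active open-label arms can identify only the difference between doses

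*Combined protocol and SAP*

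**What the plan says.** The protocol states its main question in more than one way.

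- **Drug or per-dose effect.** Section 15.1 opens with "The primary goal of the current study is to determine the effects of Aerospan on lung function in children with small airway obstruction". Section 1 proposes the study "to determine the effect of each dose on spirometry and impulse oscillometry (IOS) parameters". Section 15.2 claims "86% power to detect a 10% main effect of each treatment for each outcome".
- **Dose difference.** The synopsis objective is "To assess whether there is a dose-related difference with flunisolide HFA in pediatric patients with small airway obstruction". The synopsis efficacy evaluations, primary endpoint and primary analysis plan, and section 4.1, also compare the two dose groups.
- **Either reading.** Section 3.1 has "To assess the impact on lung function of two different doses of HFA flunisolide in asthma patients with small airway disease".

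On design, section 4.1 states "Patients will be randomized to receive flunisolide at either 80mcg twice a day or 160mcg twice a day". Sections 7.2 and 7.2.1 confirm equal allocation and open labelling. No placebo or untreated arm and no run-in are described; Baseline follows Screening by 1 to 56 days (section 9.2). There is one follow-up visit, at six weeks. Section 15.1 starts with paired t-tests of change from baseline to that visit. Mixed models follow, but their terms are not listed, so no arm-by-visit contrast is named as primary.

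**The concern.** A paired t-test asks whether patients changed, not whether the arms differ. The goal in section 15.1, its first test and the power statement in section 15.2 all point to a claim that flunisolide improved lung function at each dose. Change over six weeks also contains drift, learning of the tests, the effect of a newly supplied rescue inhaler with spacer and step-by-step instruction (sections 6 and 7.2.4), and open-label expectation. Using a correct between-arm test would not rescue the section 15.1 goal, because that test answers a different question.

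The second risk is how a null dose result would be read. Section 1.6 reports that at ages 6 to 11 "there was no added benefit for the 160 mcg BID dose over the 80 mcg BID dose" on FEV1, so a null is plausible here. It would be easy to describe it as both doses working equally well.

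**Working it through.** **1. What each contrast estimates.** Let E80 and E160 be the drug effects and D the non-drug change over six weeks.

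- Mean change in an arm = E80 + D, or E160 + D. Nothing in the design estimates D.
- Difference between arms = E160 − E80. Randomisation gives D the same expectation in both arms (setting aside any effect of knowing one's dose).

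The cited pediatric trial shows why this matters. Its active arms only maintained FEV1, and the effect was visible because placebo fell by 4.0% (section 1.6).

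**2. The plan's own figures.** Sample size: 50 × 0.9 × 0.9 = 40.5, which reproduces n = 40, so 20 per arm. The 86% cannot be checked because no SD is given. Treating the 10% as 10 points, with two-sided alpha 0.05 (stated only for the odds-ratio claim), it can be inverted using z(0.975) + z(0.86) = 3.040. Power for a 10-point dose difference is Φ(10/(SD√(2/20)) − 1.96).

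| If 86% refers to | Implied SD of change | Power for a 10-point dose difference |
|---|---|---|
| Dose contrast, 20 v 20 | 10/(3.040 × √(2/20)) = 10.4 | 86% |
| Change in one arm, n = 20 | 10/(3.040/√20) = 14.7 | 58% |
| Pooled change, n = 40 | 10/(3.040/√40) = 20.8 | 33% |

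The wording of section 15.2 suggests the second row.

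**3. Paired test in one arm with zero drug effect.** Assume a non-drug mean rise s. The test statistic is noncentral t with 19 df and noncentrality s√20/SD. The chance of a significant improvement, nominally 2.5%, is:

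| Assumed rise s | SD 10.4 | SD 14.7 |
|---|---|---|
| 2 points | 13% | 8% |
| 4 points | 37% | 21% |
| 6 points | 69% | 41% |

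**4. What a null dose result would say.** The 95% CI half-width is 1.96 × SD × √(2/20): 6.4 points at SD 10.4, 9.1 at SD 14.7 and 12.9 at SD 20.8. The interval bounds E160 − E80 and says nothing about E80 alone.

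**5. Regression to the mean in FEF25-75.** This was simulated with no drug effect: true mean 70 or 80% predicted, between-child SD 20, visit SD 8 to 15 (all assumed), entry if below 65%.

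- Only Screening selects: Baseline to week 6 changes by about 0.
- Cut-off applied at Screening and again at Baseline: Baseline to week 6 rises by about 1.7 to 7.3 points.

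The synopsis and section 8.1.1 place the qualifying spirometry at Screening. Section 9.2 randomises after Baseline spirometry if all eligibility is met, and section 11 allows eligibility to fail at Baseline. The text does not say whether the cut-off is applied again.

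**The case against.** Most statements of the objective concern the dose comparison, and the sentence after the section 15.1 goal describes the two-dose randomisation, so the goal may be loose wording. The hope in section 1 of changing practice is conditional on a dose-dependent improvement, which randomisation can support. Omitting an untreated arm is defensible, since section 1.2 calls inhaled steroids standard of care. Entry criteria exclude acute wheezing and recent infection or systemic steroids, chronic medication is to be kept stable, and spirometry has been done once before Baseline. Section 15 also promises a detailed SAP.

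Much of this stands. It makes the point one of wording rather than design, and it reduces D without removing it. It does not settle which objective the SAP author should follow, because the statistics section itself carries the uncontrolled goal, test and power claim.

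Three stronger readings are tempting and are not supported:

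- **That regression to the mean must inflate the result.** With the assumptions above, children selected below 65% rise by about 3 to 11 points from Screening to the next visit. But the endpoint is already change from Baseline, where the expected shift is about 0 unless the cut-off is re-applied there.
- **That the cited trials show a non-drug rise of about 10%.** Section 1.6 reports "Mean FEV1 at screening was 2.44 L and mean FEV1 at baseline was 2.72 L following the 2-week run-in period", which is 2.72/2.44 − 1 = 11.5%. In children, 87.5/81.2 − 1 = 7.8%. All those patients were taking flunisolide CFC during the run-in, so the rises may be largely drug effect and do not size D.
- **That a null dose result is uninterpretable.** It is a valid interval for the dose difference. For FEV1 at ages 6 to 11, section 1.6 also reports both doses better than placebo.

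**Conclusion.** The point holds as a mismatch between the goal, first test and power statement in sections 15.1 and 15.2 and what the design can identify. The dose difference is validly estimated; a drug effect at either dose is not. This follows from having two active arms and does not depend on regression to the mean.

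The size depends on assumptions. The false-improvement rate of 8% to 69% per arm assumes a non-drug rise of 2 to 6 points and the SDs implied by the plan's 86%. No figure in the documents gives the non-drug change or the SD.

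A non-significant dose difference must not be reported as efficacy at both doses. Outside support is limited: section 1.6 reports that 80 mcg was not significantly better than placebo at 12 years and over, an age range this trial includes, and section 1.7 says the pivotal trials looked only at FEV1. The documents report no placebo-controlled data for the small-airway outcomes.

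**What to change.** In sections 1, 3.1, 15.1 and 15.2:

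1. Make the between-arm difference in change from Baseline (Visit 2) to week 6, 80 v 160 mcg twice daily, the sole primary objective, in line with the synopsis.
2. Make the between-arm estimate with its 95% CI the primary analysis, in place of the paired t-tests.
3. Restate the power for that contrast, giving the SD of change and saying whether the 10% is relative or in points.
4. Label within-arm paired changes descriptive and not attributable to the drug.
5. State that a non-significant dose difference will be reported by its CI and not as evidence that both doses work.
6. State whether the FEF25-75 cut-off is applied only at Screening or again at Baseline.

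This needs only protocol and SAP wording, with no extra patients or visits. The trial gives up a per-dose efficacy claim that it cannot support, and the restated power may fall below 86% (58% or 33% for a 10-point difference if the stated figure was for within-arm or pooled change).

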TEST DRUG, DOSE AND MODE OF ADMINISTRATION	Flunisolide HFA (Aerospan™, MEDA Pharmaceuticals, Somerset, NJ) 1 or 2 inhalations administered via MDI twice daily for 6 weeks.

DURATION OF SUBJECT PARTICIPATION AND DURATION OF STUDY	Study visits will occur at screening, baseline, and 6 weeks (± 1 week). Total duration of subject participation will be up to 8 weeks. As enrollment will occur over approximately 12 months, total duration of the study is expected to be up to 14 months (12 months enrollment plus about 2 months for the last subjects to complete treatment).
Screening, enrollment, randomization and treatment	
Screening: At the Screening visit, a focused, standardized history and physical exam will be conducted by one of the physicians on the research team. Patients will also undergo pre and post bronchodilator spirometry. Spirometry values prior to the administration of bronchodilator will be used to assess patient's enrollment status.
 
Enrollment and Randomization: At the Baseline visit, patients will undergo a repeat focused, standardized history and physical exam. Spirometry and IOS will both be undertaken pre and post bronchodilator (in this order: IOS, spirometry, bronchodilator, IOS, spirometry).
 
Treatment: Subjects will receive treatments twice per day for 6 ± 3 days.

CONCOMITANT MEDICATIONS	
Allowed: All standard therapies
 
Prohibited: Other forms of ICS, LABAs

Efficacy Evaluations	Physiologic effects (change in lung function between baseline and end of treatment) and Clinical Effects (number of asthma exacerbations, asthma control scores) will be compared between subjects randomized to flunisolide HFA 1 inhalation BID and to flunisolide HFA 2 inhalations BID.
Primary endpoint	The average change in FEV1, FEF25-75% , R5, R5-R20, AX, Fres and X5 measured by spirometry and IOS during from baseline to end of treatment (6 ± 3 days) between subjects randomized to flunisolide HFA 1 inhalation BID and to flunisolide HFA 2 inhalations BID.
SECONDARY	The number of protocol-defined asthma exacerbations requiring

ENDPOINTS	treatment with oral steroids between subjects randomized to flunisolide HFA 1 inhalation BID and to flunisolide HFA 2 inhalations BID.
SAFETY EVALUATIONS	Rates of adverse events, withdrawal, adherence to treatment, rate of asthma exacerbations will be monitored.

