SAFETY MONITORING	As this is an FDA approved drug being used in approved populations at approved doses, the elements listed under "safety evaluations" as above will be tracked by the PIs but no formal data safety review board will be in place.
STATISTICS Primary Analysis Plan	The primary aim is to compare the average change in spirometric values (FEV1 and FEF _{25-75%}) and IOS values (R5, R5-R20, AX, Fres) from baseline to Week 6 from participants randomized flunisolide HFA 1 inhalation BID and to flunisolide HFA 2 inhalations BID. The change in scores from baseline to six-week follow-up will initially be compared using paired t-tests and Chi-squared tests for trend. Repeated measurements will be analyzed using generalized linear mixed-effects regression modeling (GLMM) techniques. For continuous outcomes (e.g., FEV1, FEF _{25-75%} , Fres, X5, AX, R5-R20.) the identity link function and normal distribution will be used. For count data (e.g., use of Beta-agonists, episodes of coughing, episodes of wheezing, etc.) the log link function and the Poisson distribution will be used. If we dichotomize outcomes (e.g., a Beta-agonist was used, coughing occurred, etc.) the logit link function and Bernoulli distribution will be used. Statistical analyses will be performed using SAS® Version 9.3 (SAS Institute Inc., Cary, NC).
Rationale for Number of Subjects	Based on our preliminary studies, we anticipate that 10% of all potential participants will not be eligible and/or willing to participant; and that 10% of the eligible/willing participants will be lost to follow-up. Therefore, we will recruit a total of n=50 individuals for the current study. This is a feasible sample size for the research team to recruit and enroll in the current study. Power calculations were based

on the anticipated total sample size (n=40) that will be available for complete analysis.

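### Paired t-tests are named as the initial comparison of change although the aim is to compare two independent dose arms, and the planned mixed models have no written dose contrast

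*Combined protocol and SAP*

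**What the plan says.** **Aim.** The synopsis objective is "To assess whether there is a dose-related difference with flunisolide HFA in pediatric patients with small airway obstruction". Under Efficacy Evaluations, the synopsis says that physiologic and clinical effects "will be compared between subjects randomized to flunisolide HFA 1 inhalation BID and to flunisolide HFA 2 inhalations BID". Its Primary Analysis Plan gives the primary aim as comparing average change "from baseline to Week 6 from participants randomized flunisolide HFA 1 inhalation BID and to flunisolide HFA 2 inhalations BID". Section 4.1 describes a parallel-group trial of two strengths, and section 7.2 randomises equally.

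**Other goal wording.** Section 15.1 opens with the effects of Aerospan on lung function, with no mention of a dose comparison. Section 3.1 speaks of the impact of two doses. Section 1 speaks of the effect of each dose, but also hypothesises dose-dependent improvement.

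**Analysis.** Section 15.1 states: "The primary endpoint will be changes in outcomes, over time, from baseline to six-week follow-up". It continues: "The change in scores from baseline to six-week follow-up will initially be compared using paired t-tests and Chi-squared tests for trend". The next sentence reads: "Repeated measurements will be analyzed using generalized linear mixed-effects regression modeling (GLMM) techniques". For continuous outcomes it then gives only the link function and the distribution. The synopsis repeats the test and model sentences. The between-group tests named in 15.1 (ANOVA, Kruskal-Wallis, Fisher, Wilcoxon) are there to check whether randomisation succeeded.

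**Sample size.** Section 15.2 says: "We will develop separate mixed-effects general linear models for each of the continuous outcomes". It then states that, with 40 analysable subjects, "the study has 86% power to detect a 10% main effect of each treatment for each outcome".

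**Later detail.** Section 15 promises a detailed SAP, including any modifications, before the data are analysed.

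**The concern.** The arms contain different children, so nothing pairs one dose with the other. A paired t-test asks whether subjects changed, not whether the doses differed. It is nevertheless the first test of change named, and in the synopsis it sits under the primary analysis heading. The model that could answer the dose question is described without a dose term, a dose-by-visit term or a week-6 contrast.

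Two choices are therefore left for later: which model term carries the result, and whether the t-test or the model decides. The trial is open label, so it is better to have both in writing beforehand. The power statement has the same gap, because an effect of each treatment is not evidently a difference between treatments.

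**Working it through.** **1. What each method estimates.** Let m80 and m160 be the true mean changes from baseline to week 6.

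- Target: m160 − m80.
- Paired t-test in one arm: m80 or m160.
- Paired t-test on both arms pooled, equal sizes: (m80 + m160)/2.

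The text does not say which paired version is meant; neither is the target. True changes of 10 and 10 (no dose difference) and of 5 and 15 (a 10-point difference) give the same pooled mean: (10 + 10)/2 = (5 + 15)/2 = 10. In 100,000 simulated trials with an SD of change of 20.3, the pooled paired test was significant in 86.0% of trials in the first case and 84.5% in the second. A two-sample test of change was significant in 4.9% of trials in the first case; its power in the second is 33.0%.

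**2. Why the model term must be written.** With two visits, consider intercept + dose + visit + dose × visit + subject effect. The dose × visit coefficient is m160 − m80. If only a dose main effect is fitted, it averages the arm difference over baseline and week 6. With balanced baselines and a 10-point difference at week 6, that average is (0 + 10)/2 = 5. Both models fit the description in 15.1.

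**3. The plan's own figures.** Section 15.2 allows 10% ineligible or unwilling and 10% lost: 50 × 0.9 × 0.9 = 40.5, which agrees with the stated 40. Equal allocation gives 20 per arm. The 86% cannot be reproduced, because no SD, correlation or contrast is given.

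**4. What the 86% could mean.** Assumptions: the 10% effect is 10 points; alpha is two-sided 0.05 (15.2 states this only with the odds-ratio figure); 20 completers per arm; t-test calculations stand in for the mixed model. Power comes from the noncentral t distribution, with d = 10/SD of change:

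- two-sample, 20 per arm: df = 38, noncentrality d√(20/2);
- paired, one arm: df = 19, noncentrality d√20;
- paired, all 40: df = 39, noncentrality d√40.

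Solving each for 86% gives the SD. That SD then goes into the two-sample formula for a 10-point dose difference.

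| Reading of the 86% | d | SD = 10/d | Two-sample noncentrality, d√10 | Between-dose power | Dose difference with 86% power, 0.987 × SD |
|---|---|---|---|---|---|
| Two-sample, 20 per arm | 0.987 | 10.1 | 3.12 | 86% | 10.0 |
| Paired, one arm of 20 | 0.717 | 13.9 | 2.27 | 60% | 13.8 |
| Paired, all 40 pooled | 0.493 | 20.3 | 1.56 | 33% | 20.0 |

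**5. With baseline adjustment.** In 20,000 simulated trials per setting, with the SD of change held at the values above and an assumed baseline-to-week-6 correlation of 0.5 to 0.7, ANCOVA gave between-dose power of 90–93%, 66–71% and 37–41%.

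**The case against.** The strongest reply is that this is under-specification, not a wrong analysis. The word initially marks the paired test as a first step. Section 15.2 ties the continuous outcomes to mixed models, states the 86% directly after doing so, and concludes about numbers in each comparison group. The synopsis states the dose comparison in words. Read together, the mixed models look like the main method. This stands, and it limits the point: a reader might infer that the plan cannot answer its question, but a mixed model with the right term would do so.

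Second, within-arm change fits some of the goal wording in sections 1, 3.1 and 15.1. This also stands, and it means that the aims need aligning as well as the test. It does not displace the between-dose aim, which the synopsis states three times and the parallel design supports.

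Third, a SAP is promised. It is a proper place for the contrast, but it is not among the documents, so whether the contrast was fixed before analysis cannot be judged here. The promise does not correct the test now named.

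Two stronger readings should be resisted. One is that the trial has only 60% or 33% power: those figures depend on an unstated SD, an assumed meaning of 10% across outcomes in different units, and t-test readings of a mixed-model figure, and on one reading nothing is lost. The other is that the dose conclusion would be drawn by noting significance in one arm and not the other; no passage says so.

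**Conclusion.** The point holds on the text. The initial test named for change does not match the between-dose aim. The mixed models that could serve that aim have no written dose contrast, and no sentence says which method decides. This part needs no numerical assumption.

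The 86% power cannot be verified for the dose difference. The range of 86%, 60% or 33% shows how much depends on what was calculated; it is not an estimate of the trial's power. The data to be collected can answer the question, so this should be fixed but does not undermine the design.

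**What to change.** - **Section 15.1 and synopsis, Primary Analysis Plan:** replace the paired t-test as the comparison of continuous outcomes with the 160 minus 80 mcg BID difference at week 6, adjusted for the baseline value of the same variable, with 95% CI. State whether it is fitted as ANCOVA or as the week-6 dose contrast of the planned mixed model, write that contrast out, and designate it as the deciding analysis. An unadjusted comparison of change between arms would also match the aim; baseline adjustment is preferred for precision. Keep within-arm paired changes as description.
- **Sections 15.1 and 3.1:** align the goal wording with the between-dose aim, and check section 1 against it.
- **Section 15.2 and synopsis, Rationale for Number of Subjects:** restate the power for this contrast with its assumed SD, leaving the sample size unchanged. Remove the claim of ample numbers if the restated figure does not support it.

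The cost is text edits and possibly a less favourable stated power. Spirometry and IOS are already scheduled at baseline and week 6 (sections 9.2 and 9.3), so nothing is added to visits, measurements or enrolment. The edit does not settle which lung-function variable is primary, or whether pre- or post-bronchodilator values are used; those need their own statements.
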